## 8. STUDY CALENDARS

Pre-study laboratory and exam evaluations are to be conducted within 2 weeks prior to start of protocol therapy. Pre-study scans and x-rays must be done  $\leq 4$  weeks  $\pm 1$  week prior to the start of therapy. In the event that the patient's condition is deteriorating, laboratory evaluations should be repeated within 48 hours prior to initiation of the next cycle of therapy. ***All time points on study have leeway of plus or minus 3 days unless otherwise noted.***

**NOTE:** *In order to minimize the need for research-only in-person visits, telemedicine visits may be substituted for in-person clinical trial visits or portions of clinical trial visits where determined to be appropriate and where determined by the investigator not to increase the participants risks. Prior to initiating telemedicine for study visits the study team will explain to the participant, what a telemedicine visit entails and confirm that the study participant is in agreement and able to proceed with this method. Telemedicine acknowledgement will be obtained in accordance with the Guidance for Use of Telemedicine in Research. In the event telemedicine is not deemed feasible, the study visit will proceed as an in-person visit. Telemedicine visits will be conducted using HIPAA compliant method approved by the Health System and within licensing restrictions.*

### ARM C: Nivolumab control arm (Will not continue enrollment)

|   | Pre-Study       |  | 28 day cycles (repeat) |        |        |        |                 | Follow up         |
|---|-----------------|--|------------------------|--------|--------|--------|-----------------|-------------------|
|   |                 |  | Week 1                 | Week 2 | Week 3 | Week 4 | Week 32         |                   |
| Nivolumab                       |                 |  | X                      |        |        |        | X               |                   |
| Informed Consent                            | X               |  |                        |        |        |        |                 |                   |
| History & Physical              | X               |  | X                      |        |        |        | X               |                   |
| Concurrent Meds                             | X               |  | X                      |        |        |        | X               |                   |
| CBC and Chemistry               | X               |  | X                      |        |        |        | X               |                   |
| Research Bloods                 | X               |  | X          |        |        |        |                 |                   |
| $\beta$ -HCG                                | X               |  |                        |        |        |        |                 |                   |
| AE assessment                               | X               |  | X                      |        |        |        | X               |                   |
| MRI or CT Scan of Brain                     | X               |  |                        |        |        |        |                 |                   |
| CT or MRI for Tumor Assessment  | X 5* |  |                        |        |        |        | X 5* | X 5*   |
| Tumor Biopsy                    | X               |  |                        |        |        |        |                 |                   |
| Review of medical records, telephone        |                 |  |                        |        |        |        |                 | Every 3 months up |

|  |  |            |
|--|--|------------|
| contact for recurrence-free and overall survival |  | to 5 years |
|--|--|------------|

1. 240 mg IV; After a subject has completed 6 months of nivolumab, they can receive nivolumab 480 mg every 4 weeks instead of every 2 weeks.
2. History and physical, includes interval history, oncologic driver mutation, smoking history, vital signs, oxygenation at rest and walking, height, weight, and performance status
3. Complete blood count and differential, and comprehensive metabolic panel, NOTE -TSH, Free T4 once every 28 days.
4. Plasma for assessment of methylation, peripheral blood lymphocytes for assessment of gene expression WILL BE COLLECTED PRIOR TO NIVOLUMAB ADMINISTRATION at baseline or day 1, week 5, week 9, week 17, week 25 and at progression (please see lab manual).
5. Tumor assessment includes radiologic assessment for RECISTv1.1 evaluation. Repeat radiologic assessment at week 8-9 and every 8 weeks thereafter while patient continues to receive Nivolumab. **\*During week 24, whenever that falls, tumor radiologic assessment for RECISTv1.1 evaluation for the primary endpoint will occur no matter where that falls during the cycle or treatment with nivolumab.**
6. Tumor biopsy is required prior to INITIATION OF NIVOLUMAB, and at the time of progression. Biopsy at the time of progression should be conducted as soon as possible following imaging-confirmed disease progression.

#### Arm D, E and F: Epigenetic and Nivolumab Combination Therapy

|  | Pre-study      | Cycle 1-6      |                  |                |                | Nivolumab monotherapy |        |                   |                | Follow up                    |
|--|----------------|----------------|------------------|----------------|----------------|-----------------------|--------|-------------------|----------------|------------------------------|
|  |                | Week 1         | Week 2           | Week 3         | Week 4         | Week 1                | Week 2 | Week 3            | Week 4         |                              |
| Azacytidine   |                | d 1 - 5        | d 8 - 10         |                |                |                       |        |                   |                |                              |
| Entinostat    |                | d 3            | d 10             |                |                |                       |        |                   |                |                              |
| Nivolumab    |                | D1             |                  | D15            |                | D1                    |        | D15  |                |                              |
| Informed Consent  | X              |                |                  |                |                |                       |        |                   |                |                              |
| History & Physical    | X              | X              |                  | X              |                | X                     |        | X    |                |                              |
| Concurrent Meds   | X              | X              | X                |                |                | X                     | X      |                   |                |                              |
| CBC and Chemistry   | X              | X              | X                | X              |                | X                     |        | X    |                |                              |
| Research Bloods   | X              | X  |                  |                |                | X         |        |                   |                |                              |
| β-HCG   | X              |                |                  |                |                |                       |        |                   |                |                              |
| AE assessment   | X              | X              | X                | X              |                | X                     |        | X    |                |                              |
| CT or MRI for Tumor Assessment    | X              |                |                  |                | X              |                       |        |                   | X              |                              |
| MRI or CT with contrast of Brain  | X              |                |                  |                |                |                       |        |                   |                |                              |
| Tumor Biopsy  | X  |                | X  | X  | X  |                       |        |                   | X  |                              |
| Review of medical records, telephone contact for recurrence-free and overall survival |                |                |                  |                |                |                       |        |                   |                | Every 3 months up to 5 years |

1. 40 mg/m2 s.c. days 1 – 5 and 8 – 10
2. 5 mg PO days 3 and 10
3. History and physical, includes interval history, oncologic driver mutation, smoking history, vital signs, oxygenation at rest and walking, height, weight, and performance status
4. Complete blood count and differential, comprehensive metabolic panel, serum magnesium and serum phosphate. Note-TSH, Free T4 once every 4 weeks.

5. Plasma for assessment of methylation, peripheral blood lymphocytes for assessment of gene expression WILL BE COLLECTED PRIOR TO TREATMENT ADMINISTRATION at baseline or day 1, week 5, week 9, week 17 and week 25 and at progression (please see lab manual).
6. Tumor assessment at all later time points include radiology scans to be performed every 8 weeks. The window is +/- 1 week.
7. Tumor biopsy required prior to treatment initiation.
8. Required on treatment biopsy should be performed during Cycle 2 Week 2 or 3 FOLLOWING completion of epigenetics for that cycle; must be completed prior to Cycle 3 dosing.
9. Required biopsy at time of disease progression while on combination therapy or nivolumab monotherapy per patient course. Biopsy at the time of progression should be conducted as soon as possible following imaging-confirmed disease progression.
10. After a subject has completed 6 months of nivolumab, they can receive nivolumab 480 mg every 4 weeks instead of every 2 weeks. Day 15 lab assessments, history and physical and AE assessments are not required for patients receiving nivolumab every 4 weeks. These assessments will be captured on day 1 of every cycle for subjects on Nivolumab every 4 weeks.

## 9. MEASUREMENT OF EFFECT

### 9.1 Antitumor Effect – Solid Tumors

On this study, planned radiologic evaluations will be performed at baseline (within 4 weeks prior to starting study therapy) and then every 8 weeks. For all Arms, confirmatory scans should be obtained not less than 4 weeks following initial documentation of objective response, and will typically be obtained at the time of the next planned evaluation (i.e. 8 weeks following).

Response and progression will be evaluated in this study using the new international criteria proposed by the revised Response Evaluation Criteria in Solid Tumors (RECIST) guideline (version 1.1) [Eur J Ca 45:228-247, 2009]. Changes in the longest diameter (unidimensional measurement) of the tumor lesions and the shortest diameter in the case of malignant lymph nodes are used in the RECISTv1.1 criteria. RECIST readers will be blinded to the treatment assignment of all subjects.

Accumulating evidence indicates that the emergence of objective responses to agents that activate anti-tumor immune responses may follow delayed kinetics of weeks or months, and can be preceded by initial apparent radiological progression, or the appearance of new lesions or some enlarging lesions while certain target lesions are regressing (“mixed response”). It is thus reasonable, in the absence of clinical deterioration, to continue to treat these subjects until radiologic progression is **both** confirmed **and** found to have worsened at a subsequent imaging evaluation. Evidence of PD will be based on a comparison with baseline (or nadir) scans, in which there is either an increase of 20% or more in the sum of the longest diameters (SLD) of target lesions taking as reference the smallest sum of the longest diameters (nadir) recorded since starting nivolumab treatment, and/or unequivocal progression of non-target lesions, with or without the development of 1 or more new lesions. PD should be confirmed by repeat scans at the next scheduled imaging evaluation 8 weeks later (but no sooner than 4 weeks).

Subjects with PD should be managed in the study as per Section 4.4.1.

#### 9.1.1 Definitions

Evaluable for toxicity. All patients will be evaluable for toxicity from the time of their first treatment on protocol.

Evaluable for objective response. Response to azacitidine/entinostat and to Nivolumab, will be assessed separately. For each, only those patients who have measurable disease present at baseline, have received at least one cycle of therapy, and have had their disease re-evaluated will be considered evaluable for response. These patients will have their response classified according to the definitions stated below. (Note: Patients who exhibit objective disease progression prior to the end of the first cycle of either therapy will also be considered evaluable.)

Evaluable Non-Target Disease Response. Patients who have lesions present at baseline that are evaluable but do not meet the definitions of measurable disease, have received at least one cycle of therapy, and have had their disease re-evaluated will be considered evaluable for non-target disease. The response assessment is based on the presence, absence, or unequivocal progression of the lesions.

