## 2.4 Rationale for combining epigenetic therapy with immunotherapy

### 2.4.1 Clinical Rationale for combination epigenetic and immunotherapies

Due to 2015 FDA-approval of nivolumab in the 2nd line treatment setting of advanced or metastatic NSCLC, this protocol was previously amended to update nivolumab administration to be given concurrently starting at the initiation of combination study treatment. Therefore, for those patients randomized to combination therapy, nivolumab will be given in combination with epigenetic therapy for 6 cycles, followed by nivolumab monotherapy until disease progression. This will provide patients treated with maximal exposure to both epigenetic therapy and the immune checkpoint inhibitor, in keeping with standard of care practice. In this manner, patients will have longer exposure to the

potential benefits of both epigenetic therapy and immune checkpoint inhibition. This update in therapy is further supported by data indicating that 58.3% (14/24) patients were unable to receive two months of epigenetic therapy alone ("priming") prior to initiation of nivolumab in an earlier therapeutic intervention in this trial (Arm A), due to both symptoms (nausea, vomiting, fatigue, pain) and subsequent rapid disease progression on epigenetic therapy alone.

[figure not shown]
Importantly, the concurrent administration of epigenetic therapy and immune checkpoint inhibition is hypothesized to quickly combine the immune attraction signals from epigenetic therapy with the initial immune-tolerance inhibiting activity of immune checkpoint blockade, and allow the patient's tumor to be exposed to this interaction for a longer and perhaps more significant length of time than in the previous treatment arm. This is supported by pre-clinical data for the combination of these agents' mechanisms of action on efficacy and overall tolerability as detailed below.

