##### 10.1.2 Endpoints

##### **Primary Endpoint**

##### Overall response rate (ORR)

Response, by Arm, will be measured per RECIST 1.1, as described in Section 9.

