## **Secondary Endpoints**

### Progression free survival

Progression-free survival (overall) will be measured from the time of first dose of therapy until radiologic or clinical progression is noted or death from any cause.

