## **10.2 Sample size, Analysis, and Accrual Rate**

The study will enroll up to 20 patients on Arm D, 20 patients on Arm E and 20 patients on Arm F. With this amendment, there will be no further enrollment for treatment on Arm C, although these patients will be allowed to cross over to Arms E or F if they progress and are otherwise eligible. The sample size is driven by what we think is feasible for enrollment over a reasonable period of time (e.g., a few years). We are including futility analyses within each Arm to allow us to stop a treatment arm if it appears not to have enough activity to warrant further investigation. Additionally, we have interim analyses to assess the feasibility of continuing an arm, with feasibility defined in the previous subsection.

The final analysis for each arm will be descriptive, consisting of summary statistics and confidence intervals. We will use survival analysis methods (e.g., the Kaplan-Meier survival estimation) for time-to-event data. We will not adjust for multiple comparisons; the futility analyses do not inflate the type I error, as seen in the simulation results (see section 10.4). Allowing for up to 10% invaluable patients, we will enroll up to 22 patients on each Arm, or a total of 66. Anticipated accrual rate is 5 patients per month.

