### 10.4 Interim Analyses

The study design calls for interim futility analysis by arm. These analyses will occur separately by arm once 10 patients are on an arm and have either received at least 6 cycles of therapy or experienced a PFS event. Subsequent analyses will occur after 15 patients have either received at least 6 cycles of therapy or experienced a PFS event. The final analysis will occur after 20 patients have entered and received full therapy (6 cycles). The futility analysis is based on Bayesian hypothesis testing.

For Arm D, we take the expected ORR to be 20% if epigenetic therapy does not increase the clinical effectiveness of nivolumab alone. This estimate is based on results of the Checkmate studies (CheckMate 057 (non-squamous NSCLC) ORR = 19%; CheckMate017 (squamous cell NSCLC) ORR = 20%). We would consider the addition of epigenetic therapy encouraging if the ORR is 35% or higher. The study will stop for futility if we see 0 responses among the first 10 patients or no more than 1 response in the first 15 patients. We will not consider this Arm promising if we see 3 or fewer responders out of 20 patients. The following table provides the operating characteristics for Arm D based on 5000 simulations.

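### The primary response rate can leave out treated patients who are never re-scanned, and Sections 9.1.1 and 10.4 count patients on conflicting bases

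*Combined protocol and SAP*

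**What the plan says.** - Section 10.1.2 defines the primary endpoint by reference: "Response, by Arm, will be measured per RECIST 1.1, as described in Section 9".
- Section 9.1.1 restricts response evaluability to "only those patients who have measurable disease present at baseline, have received at least one cycle of therapy, and have had their disease re-evaluated". Its one exception reads "Patients who exhibit objective disease progression prior to the end of the first cycle of either therapy will also be considered evaluable".
- Sections 8 and 9.1 schedule repeat imaging every 8 weeks; the Section 8 calendar gives a window of one week either side.
- Section 10.2 allows for up to 10% unevaluable patients on top of 20 per arm: "we will enroll up to 22 patients on each Arm, or a total of 66".
- Section 10.4 places the looks when 10 and then 15 patients in an arm "have either received at least 6 cycles of therapy or experienced a PFS event". Section 10.1.2 runs PFS "until radiologic or clinical progression is noted or death from any cause", so deaths and clinical progressions count as events.
- For the last analysis Section 10.4 says: "The final analysis will occur after 20 patients have entered and received full therapy (6 cycles".
- The Arm D bars in Section 10.4 are: stop at 0 responses in 10 or at most 1 in 15, and not promising at 3 or fewer in 20. The reference rate is 20% and the encouraging rate is 35%.
- No section says how a treated patient without any repeat assessment enters the response rate.

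**The concern.** A patient who is never re-scanned cannot be a RECIST responder. If the reason is death, clinical decline or leaving treatment early, leaving the patient out makes the denominator depend on outcome, always in the regimen's favour. These are uncontrolled arms of 20, and Arm D is judged against a fixed 20% reference, so a few such patients matter.

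The plan also does not say which patients the 10-, 15- and 20-patient bars apply to. Two analysts following different sections could reach different decisions from the same data. Section 9.1.1 still assesses response to azacitidine/entinostat and to nivolumab separately, which does not fit concurrent treatment and suggests that the definition was carried over from a previous design.

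**Working it through.** **1. The counting rules side by side**

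| Treated patient | Evaluable (9.1.1) | Counts toward the 10/15 looks (10.4) | Counts toward the final 20, read literally (10.4) |
|---|---|---|---|
| Dies in week 5, no repeat scan | No | Yes (PFS event) | No |
| Clinical progression in week 6, no repeat scan | No | Yes (PFS event) | No |
| Leaves all treatment for toxicity in week 6, no repeat scan | No | Not until a PFS event | No |
| Objective progression at the week-8 scan, then stops | Yes | Yes | No |

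No two columns agree.

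**2. Reproducing the plan's figures**

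Exact binomial recursion for Arm D at a true rate of 20%:
- stop at 10: 0.8^10 = 0.107
- stop at 15: 0.088
- 3 or fewer at 20: 0.234
- total: 0.4295, against 0.434 printed in 10.4

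The chance of being called promising is 1 - 0.4295 = 0.5705. At 35% the recursion gives 0.053 against 0.047 printed. For Arms E and F at 10%, 0.9^15 = 0.2059 against 0.206. The printed tables therefore correspond to counting every patient.

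**3. Direction**

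Let p be the response rate in all treated patients and u the share never re-scanned. The evaluable-only rate is p/(1 - u), which is never below p. At u = 10%, 0.20/0.90 = 22.2% and 0.35/0.90 = 38.9%.

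**4. Size for Arm D with the 22-patient cap**

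Each treated patient is a responder (probability p), never re-scanned (u), or a scanned non-responder (1 - p - u). Enrolment stops at 20 evaluable or 22 treated. If 22 are treated and fewer than 20 are evaluable, the bar stays at 4 responders. Two readings are computed exactly:
- (a) the looks count all treated patients, as 10.4 implies for deaths and clinical progressions, and only the final analysis is evaluable-only;
- (b) evaluable-only at every look.

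| True rate p | Assumed u | Promising, (a) | Promising, (b) |
|---|---|---|---|
| 20% | 0 | 57.0% | 57.0% |
| 20% | 5% | 60.2% | 61.0% |
| 20% | 10% | 62.0% | 63.7% |
| 20% | 20% | 63.2% | 65.9% |
| 15% | 0 | 33.8% | 33.8% |
| 15% | 10% | 38.2% | 39.5% |
| 35% | 0 | 94.7% | 94.7% |
| 35% | 10% | 96.1% | 96.8% |

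The gain flattens because the cap admits at most two extra patients. Under (a) at p = 20% the ceiling is the chance of passing both looks and then having at least 4 responders among 22, which is 63.3%.

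**5. Arms E and F at a true 10%**

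Under (a) nothing changes (79.4%), because an arm that passes 0/15 already has a response. Under (b) it becomes 81.1% at u = 5% and 82.9% at u = 10%.

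**6. The reported rate**

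With 22 treated and 2 dropped, 7/20 = 35.0% reaches the encouraging level while 7/22 = 31.8% does not. Likewise 4/20 = 20.0% against 4/22 = 18.2%.

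**The case against.** The strongest reply is that the denominator is unclear rather than wrongly chosen. Section 10.1.2 refers to Section 9 for how response is measured, and 10.4 speaks of the first 10, the first 15 and 20 patients without an evaluability qualifier. The final analysis is descriptive, and two exclusions move the estimate little against the uncertainty at 20 patients. PFS, survival, toxicity and feasibility monitoring would also show early failures. All of this is fair, and it limits the weight of the point. It does not remove it: 9.1.1 is the only stated rule on who enters the response rate, and the extra enrolment in 10.2 presupposes that some patients will not.

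The excluded group may also be small:
- Eligibility requires a life expectancy above 12 weeks and ECOG 0 to 1.
- Section 4.4 lets patients with adverse events go on with nivolumab alone after 2 cycles, so many of them would still be scanned.
- Sections 4.4.1 and 9.1.4.3 ask that progression be documented after treatment stops, and a patient with one cycle and a later scan is evaluable.

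These points reduce u, but they set no rule for the patient who is never scanned.

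Four stronger inferences are not supported:
- A reader might apply p/(1 - u) at every look with unlimited replacement, giving 66% at 10% and 76% at 20%. That ignores the cap of 22 and, for deaths and clinical progressions, the counting rule in 10.4.
- A reader might infer that the 0/15 stop in Arms E and F is delayed. Deaths and clinical progressions count toward the 15 under 10.4, so they cause no delay.
- A reader might take Arm A's experience ("58.3% (14/24) patients were unable to receive two months of epigenetic therapy alone") as the loss rate. It comes from a sequential regimen without concurrent nivolumab and is not a rate of unscanned patients. It shows only that early loss is plausible.
- A reader might treat the whole 10% allowance as early failures. The plan does not say so, and some could be unrelated to outcome.

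**Conclusion.** The point holds. As written, 9.1.1 removes treated patients who are never re-scanned from the primary response rate, and 10.4 uses two further counting bases that do not match it or each other. The direction is certain: the rate can only rise or stay the same.

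The size is modest. At a true Arm D rate of 20% and with 10% excluded, the chance of being called promising rises by about 5 to 7 points, from 57% to 62-64%. At a true 15% it rises from 34% to about 38-40%. These figures assume that every excluded patient is an unscanned non-responder and that enrolment stops at 22. The value of u is an assumption throughout, because the documents give no early-loss rate for Arms D to F.

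The documents do not show an intention to discard failures. The inconsistency is still worth settling, because it bears on the primary endpoint and on the go/no-go bars.

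**What to change.** In Sections 9.1.1, 10.2 and 10.4:
- Define the primary denominator as all patients in the arm with measurable baseline disease who received a first dose, in order of entry.
- Count anyone without a post-baseline assessment as a non-responder.
- Apply the 10-, 15- and 20-patient bars to the first 10, 15 and 20 such patients.
- Replace the full-therapy condition for the final analysis with the interim one (6 cycles or a PFS event), and add patients who are otherwise off treatment.
- Report the final response rate over all treated patients, with the evaluable-only rate as supplementary.

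The cost is wording. No new data or patients are needed, and the operating characteristics printed in 10.4 then apply as they stand. The reported rate may be slightly less favourable.
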